4.8.2 Thrombosis Events

Number of thrombosis events will be summarized for the Safety, Evaluable and PP populations, at each column size and blood-flow rate combination. A listing will also be provided.

4.8.3 Weight

Weight will be collected as described in the Schedule of Events, Protocol Section 15.1. Observed values in kg, will be tabulated at pre-HD and post-HD per HD session. Change from pre-HD at post-HD per HD session will also be summarized. Summaries will be provided for the Evaluable and PP populations.

Interdialytic weight gain will also be calculated as:

Statistical Analysis Plan AKST1210-101

Rev. A Page 18 of 28

Interdialytic weight gain (kg) = Pre-HD weight (kg) – post-HD weight (kg) from previous HD session.

Interdialytic weight gain will be provided in a listing and will be summarized by visit and each column size/blood-flow rate combination.

A listing of weight (kg) will be provided.

4.8.4 **b2M**

Plasma b2M levels will be measured at V4 (baseline), V7, V10, V13, V16, V19, V22, and V23. At V4 and V23 (EOS), one blood sample will be collected at the arterial port pre-HD. Summaries will be provided for the b2M population.

At V7, V10, V13, V16, V19, and V22, blood samples will be collected at two locations: arterial port and venous port. At the arterial port, samples will be collected pre-HD, 15 min into HD, mid-HD, and end-HD. At the venous port, samples will be collected 15 min into HD, mid-HD, and end-HD.

Research question 1: Is the b2M overall removal different between the different flow rates for each column?

Research question 2: Is the b2M overall removal different between the column sizes at each flow rate?

Analysis methods: a mixed-effect model for repeated measures (MMRM) will be performed at the whole study group for the changed b2M levels (comparing to levels at V4) at arterial port at V7, V10, V13, V16, V19, and V22, with fixed effect of flow rates (binary), column size (categorical) and flow rates-column size interaction, baseline b2M levels, and random effect of intercept and sites (or dialyzer types). Least-square means of changed b2M levels and associated 95% CI at each flow rate and at each column size will be calculated based on the analysis. The comparisons of estimated changed b2M levels between flow rates in each column size will be conducted, which answer question 1. The pair-wise comparisons of estimated changed b2M levels between column sizes at each flow rate will be conducted, which answer question 2. We will use Pre-HD arterial b2M levels to calculate overall removal from baseline for each time point.

Research question 3: Is b2M instantaneous clearance different between the different flow rates for each column?

Research question 4: Is b2M instantaneous clearance different between the column sizes at each flow rate?

Analysis methods: a mixed-effect model for repeated measures (MMRM) will be performed at the whole study group for the b2M ratios (levels at venous port/levels at arterial port) in the logarithmic scale after 15 min, at mid-HD and end-HD at V7, V10, V13, V16, V19, and V22, with fixed effect of flow rates (binary), column size

Statistical Analysis Plan AKST1210-101

Rev. A Page 19 of 28

(categorical), flow rates-column size interaction, time (categorical, after 15 min, at mid-HD and end-HD), time-flow rates interaction, time-column size interaction, time-flow rates-column size three-way interaction and baseline b2M levels, and random effect of intercept and sites (or dialyzer types). Least-square means of the 3 b2M ratios and associated 95% CI at each flow rate and at each column size will be calculated based on the analysis. The comparisons for each of 3 estimated b2M ratios between flow rates in each column size will be conducted, which answer question 3. The pair-wise comparisons for each of 3 estimated b2M ratios between column sizes at each flow rate will be conducted, which answer question 4. The comparisons would be repeated for each measuring time-point (after 15 min, at mid-HD and end-HD).

Research Question 5: Is there a significant difference in the arterial port end-HD/pre-HD b2M removal ratios for V7, 10, 13, 16, 19, 22?

Analysis methods: a mixed-effect model for repeated measures (MMRM) will be performed at the whole study group for the end-HD/pre-HD arterial ratio in the logarithmic scale, with fixed effect of visits (V7, 10, 13, 16, 19, 22), baseline protein levels, and random effect of intercept and sites (or dialyzer types). Least-square means of end-HD/pre-HD arterial ratios and associated 95% CI at two visits will be calculated based on the model. P value testing whether the difference is equal to 0 will be provided, which indicates whether there is a significant difference in instantaneous removal ratios for V7, 10, 13, 16, 19, and 22.

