7.1.1.1.6. Hemodialysis

Beginning at run-in, HD will be conducted 3 times weekly at different blood-flow rates (see Section 4.1). The following key dialysis parameters will be captured during each HD treatment: arterial, venous, and transmembrane pressures every 30 minutes (from the HD machine; mmHg), mean and maximum blood flow rate (mL/min), reasons for changes in blood-flow rate, dialysis time (min), and type of dialyzer. Adequate safety precautions should be employed prior to and throughout HD, particularly for subjects who are at risk for developing IDH. Refer to Table 1 in

Section 2.2.1 for risks associated with the strategies.

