2.4 Secondary Endpoints

- Weekly fractional urea clearance (Kt/V) and urea reduction ratio (URR).
- Total fluid balance for each column-size flow-rate combination.
- Proportion of subjects who are able to achieve the dry weight goal during the allotted HD duration for each column size and flow rate combination.
- Change in plasma b2M concentrations (before and after HD) and contribution of the column to b2M removal at each column size and blood-flow rate.
- Number of occurrences of visible thrombosis (clotting) in the dialyzer, and/or tubing.
- Changes in plasma levels of complement factors, including total hemolytic complement (CH50), soluble membrane attack complex (SC5b-9), and C5a.

Changes in plasma levels of other proteins, including insulin, adrenocorticotropic hormone (ACTH), insulin-like growth-factor binding protein 1 (IGFBP1), Gastrin,

Osteocalcin, Parathyroid hormone (PTH), and Thyroid stimulating hormone (TSH).

3 Study Overview

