The duration of HD time will be adjusted for flow rate (approximately 4-6 hours for 250 mL/min, 3-4 hours for up to 450 mL/min). During each HD session, measurements of HD effectiveness will include Kt/V>1.2 (calculated from measurements of blood urea) and URR (weekly URR >65%).

The mean and max blood flow rate will be calculated/pulled from the entries on the HDE CRF rather than the HD CRF.

The incidence of IDH events, as defined in Protocol Appendix 17.1: Escalation, Deescalation, and Discontinuation Rules for Treatment with the Column, will be one factor used to determine column size/blood-flow rate escalation/de-escalation as well as discontinuation from the study.

The planned duration of subject participation is approximately 12 weeks (up to 4 weeks for screening and 8 weeks on-study, which is inclusive of the 1-week run-in period).

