Model diagnostics including residual and noniterative influence analysis will be conducted to ensure the MMRM assumptions (e.g., residual normality, and homogeneity of variance) and to identify potential outliers and influential observations. If residuals are not normal, logarithmic transformation will be applied to raw b2M levels before MMRM. No multiple comparison corrections will be performed as this study only aims to find trends in secondary endpoints instead of confirmation.

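### SAP 4.8.4 asks whether b2M clearance differs by flow rate but analyses the venous/arterial ratio, which reflects per-pass extraction and can point the opposite way to clearance

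*SAP*

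**What the plan says.** SAP 4.8.4 (b2M) poses five research questions. The third is "Research question 3: Is b2M instantaneous clearance different between the different flow rates for each column". The outcome modelled is the "b2M ratios (levels at venous port/levels at arterial port) in the logarithmic scale", measured at 15 minutes, mid-session and end of session at Visits 7, 10, 13, 16, 19 and 22. Flow enters the model only as a two-level fixed effect, with its interactions. The SAP then states how the question is settled: "The comparisons for each of 3 estimated b2M ratios between flow rates in each column size will be conducted, which answer question 3".

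The related secondary endpoint (SAP 2.4) covers change in plasma b2M and the column's contribution to "b2M removal at each column size and blood-flow rate". Protocol 7.1.1.1.6 has mean and maximum blood flow captured at each session, and SAP 3.1 says where they come from: "The mean and max blood flow rate will be calculated/pulled from the entries on the HDE CRF rather than the HD CRF". Neither enters the outcome for question 3. Nothing in the public text defines or derives a b2M clearance in mL/min.

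**The concern.** V/A has no units. It gives the fraction of b2M still in the blood after one pass between the two sampling ports. Clearance is a volume per unit time and needs the flow as a multiplier. Having flow as a model term does not supply that multiplier: the term tests whether extraction differs between flows, not whether clearance does.

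For most comparisons the distinction would be minor, but here flow is the factor under test. Faster flow gives less contact time per pass, so V/A may well rise while more blood is treated each minute. A reader who follows the SAP could then report that higher flow leaves b2M clearance unchanged, or lowers it, when it has raised it. The trial exists to assess the column above 250 mL/min, so the direction of this comparison matters.

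**Working it through.** The plan gives no numerical figure for b2M extraction or clearance, so there is nothing of its own to reproduce. The check asks what the ratio contrast implies for clearance.

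**Inputs**
- Flows compared: 250 and up to 450 mL/min (SAP 3.1; Protocol 4.1).
- V/A: not given. Values of 0.40 to 0.80 at 250 mL/min are assumed.
- Clearance: K = Q × (1 − V/A), ignoring ultrafiltration.

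**1. Same ratio at both flows.** With V/A = 0.50, K is 250 × 0.50 = 125 and 450 × 0.50 = 225 mL/min. The ratio contrast is 0.50/0.50 = 1.00. Clearance differs by 225/125 = 1.80.

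**2. Reversal.** With V/A 0.50 at 250 and 0.65 at 450, the ratio is 0.65/0.50 = 1.30, which is 30% worse. Clearance at 450 is 450 × 0.35 = 157.5, and 157.5/125 = 1.26, which is 26% better.

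**3. Break-even.** Clearance is equal when V/A at 450 = 1 − (250/450) × (1 − V/A at 250).

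| V/A at 250 | Break-even V/A at 450 |
|---|---|
| 0.40 | 0.667 |
| 0.50 | 0.722 |
| 0.60 | 0.778 |

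Any V/A at 450 between the two figures in a row gives a worse ratio and a higher clearance. At break-even itself the clearances are equal but the log ratios are not. From 0.50, the difference is ln(0.722/0.50) = 0.37, which the plan would read as a clearance difference.

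**4. A simple mass-transfer model.** Assume V/A = exp(−c/Q), with c = −250 × ln(V/A at 250).

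| V/A at 250 | V/A at 450 | Ratio change | K at 250 | K at 450 | K change |
|---|---|---|---|---|---|
| 0.40 | 0.601 | ×1.50 | 150 | 179.5 | ×1.20 |
| 0.50 | 0.680 | ×1.36 | 125 | 143.8 | ×1.15 |
| 0.60 | 0.753 | ×1.25 | 100 | 111.2 | ×1.11 |
| 0.80 | 0.883 | ×1.10 | 50 | 52.5 | ×1.05 |

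The two measures have opposite signs in every row.

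**5. Lower attained flow.** The high rate may be adjusted below 450. At 300 mL/min, under the same model:
- From 0.40, V/A becomes 0.466 (×1.17) and K 160.2 (×1.07).
- From 0.80, V/A becomes 0.830 (×1.04) and K 50.9 (×1.02).

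The effects are smaller, but the signs are still opposite.

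**The case against.** **Removal is analysed elsewhere.** The endpoint in SAP 2.4 is removal, not clearance. Question 1 compares pre-session arterial change between flows, and question 5 compares end-to-start arterial ratios across visits. This is true, so the removal endpoint does not rest on question 3 alone. But both depend on session length, which the design changes with flow (about 4–6 hours at 250, 3–4 hours at up to 450). Neither measures clearance.

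**Clearance is not removal either.** At midpoint session lengths, 3.5/5 = 0.70. A clearance gain of 5% to 20% then gives 0.70 × 1.05 = 0.74 to 0.70 × 1.20 = 0.84 of the per-session clearance volume. This stands as a caution: K answers question 3 and should be read with session time. It does not make V/A a clearance.

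**The b2M population limits flow deviations.** SAP 4.2.3 excludes documented deviations beyond ±20 mL/min from the specified rate. If that rate is 450, the 300 mL/min case drops out. The contrast then lies between 430/270 = 1.6 and 470/230 = 2.0, so the main problem remains. How the rule applies to a rate set as up to 450 is not stated.

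**The figures are hypothetical.** This is fair. Identical V/A at both flows cannot arise under the mass-transfer model if there is any removal, so the 80% case is a limiting illustration. Whole-blood flow was used although b2M is measured in plasma.

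**Clearance can be approximated from the planned output.** A reader could compute Q × (1 − ratio) from the reported means. That gives point estimates, but the planned contrast still concerns extraction, and the SAP says that contrast answers the question.

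**It is secondary.** The SAP says "this study only aims to find trends in secondary endpoints instead of confirmation". That supports omitting a multiplicity correction. A search for trends still needs the right sign.

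**Clearance may be defined elsewhere.** Protocol 7.1.1.3.1 is blank in the public text, and the table shells are separate files. A definition there cannot be excluded, but it would conflict with the explicit statement in SAP 4.8.4.

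**Conclusion.** The concern holds. Question 3 and its outcome do not match, and the stated analysis can be null or reversed when clearance differs. For the same V/A, clearance at 450 is 1.8 times that at 250. Under the mass-transfer assumption, with V/A of 0.40 to 0.80 at 250, the ratio looks 50% to 10% worse while clearance is 20% to 5% higher. These sizes rest on assumed V/A values, whole-blood flow and no ultrafiltration. The mismatch itself follows from the definition of clearance and needs none of the assumed values.

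The reach is limited to question 3. Question 4 compares column sizes at the same nominal flow, so flow roughly cancels unless the attained high rate differs between weeks. The sample size, the escalation rules and the primary analysis are untouched. The point should be corrected, but it does not threaten the trial.

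**What to change.** For question 3, make the outcome K = Q × (1 − V/A) at 15 minutes, mid-session and end of session, with the same model terms. The SAP should state:
- which flow is used: the recorded flow nearest each sample if available, otherwise the session mean;
- whether Q is blood or plasma flow, and how ultrafiltration is handled;
- the analysis scale, since a measured V/A of 1 or more makes K zero or negative and rules out a log.

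Keep log(V/A) as a supporting result labelled extraction. The minimum alternative is to reword question 3 as per-pass extraction and draw no clearance conclusion from it.

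The cost is SAP text and programming. Mean flow is already captured and both ports are already sampled. Flow at the b2M sampling times is not clearly documented, so the session mean may be the only choice. The drawback is that K inherits error in recorded flow. In the 0.50/0.65 example, a 10% error in the high flow gives 405 × 0.35/125 = 1.13 to 495 × 0.35/125 = 1.39, so the 26% gain becomes 13% to 39% and keeps its sign. Rewording alone costs one sentence.

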4.8.5 Complement Factors

Actual values and changes from baseline in plasma levels of complement factors, including total CH50, SC5b-9, and C5a, will be summarized by visit for the Safety and Evaluable populations.

4.8.6 Other Plasma Proteins

Actual values and changes from baseline in plasma levels of insulin, adrenocorticotropic hormone (ACTH), insulin-like growth-factor protein 1 (IGFBP1), Gastrin, Osteocalcin, Parathyroid hormone (PTH), and Thyroid stimulating hormone (TSH) will be summarized for the Safety and Evaluable populations, by visit, at each column size and blood-flow rate combination.

Other proteins will be measured at V4 (baseline), V7, and V22. At V7 and V22, these proteins will be measured only at the arterial port before and after HD.

Research question 1: Does treatment significantly remove other proteins? If yes, are there significant differences in removal between V7 and V22?

Analysis methods: mixed-effect models for repeated measures (MMRM) will be performed at the whole study group for changed protein levels after HD at V7 and V22, with fixed effect of visits (V7 vs. V22), baseline protein levels, and random

Statistical Analysis Plan AKST1210-101

Rev. A Page 20 of 28

effect of intercept and sites (or dialyzer types). Least-square means of changed protein levels associated 95% CI at two visits will be calculated based on the model. P value testing whether the LS means at each visit is significantly different from 0 will be provided, which indicates whether the treatment significantly removed these proteins. The difference in LS means between the two visits and 95% CI of the difference will also be calculated. P value testing whether the difference is equal to 0 will be provided, which indicates whether there is a significant difference in protein removal at V7 and V22.

Research question 2: Are the instantaneous removal ratios of other proteins different at V7 and V22?

Analysis methods: mixed-effect model for repeated measures (MMRM) will be performed at the whole study group for the End-HD/Pre-HD ratio in the logarithmic scale, with fixed effect of visits (V7 vs. V22), baseline protein levels, and random effect of intercept and sites (or dialyzer types). Least-square means of End-HD/Pre-HD ratios and associated 95% CI at two visits will be calculated based on the model. The difference in LS means between the two visits and 95% CI of the difference will also be calculated. P value testing whether the difference is equal to 0 will be provided, which indicates whether there is a significant difference in instantaneous removal ratios between V7 and V22.

Model diagnostics including residual and noniterative influence analysis will be conducted to ensure the MMRM assumptions (e.g., residual normality, and homogeneity of variance) and to identify potential outliers and influential observations. If residuals are not normal, logarithmic transformation will be applied to raw b2M levels before MMRM. No multiple comparison corrections will be performed as this study only aims to find trends in secondary endpoints instead of confirmation.

4.9 Other Safety Analyses

Other safety analyses include physical examination, ECG, vital signs, pregnancy tests, laboratory data, fluid assessment, prior and concomitant medications, heparin infusion, and study device accountability. Except where indicated, safety parameters will be summarized for the Safety population, by column size and blood-flow rate combination.

4.9.1 Physical Examination

Physical Examinations and targeted physical examinations will be conducted at Visit 1, and all post-baseline visits, as described in the Schedule of Events, Protocol Section 15.1.

The number and percentage of subjects with abnormal physical examination results will be summarized by the body systems.

Statistical Analysis Plan AKST1210-101

Rev. A Page 21 of 28

4.9.2 12-lead ECG

A 12-lead ECG will be performed to obtain heart rate (beats/min), QT (msec), and QT interval corrected by the Fridericia formula (QTcF (msec)). ECGs will be collected at Visit 1 and Visit 23 End of Study.

Observed value at baseline and Visit 23, along with the change from baseline value will be summarized.

A listing of all 12-lead ECG will be provided. A listing of abnormal 12-lead ECG will also be provided.

4.9.3 Vital Signs

Vital signs, including blood pressure (mmHg), heart rate (beats/min), respiratory rate (breaths/min), and body temperature (C), will be summarized. Seated/reclined BP will be recorded before each dialysis session, every 30 minutes during dialysis, and at the end of the session. Other vital signs will be captured at the beginning and end of each visit. If screening and/or EOS occur on a day in which a subject is not receiving HD, vital signs will be measured after the subject has been seated/reclined for ~5 minutes. Observed values will be tabulated at baseline, and at each scheduled post-baseline time point. Change from baseline at each scheduled post-baseline time point will also be summarized. Change from baseline in blood pressure will also be presented in figures.

Additionally, a 'Repeated SBP < 90 mmHg or action taken to HD' listing will be populated if there are two SBP < 90 within 30 minutes of the start of the HD, or if in the HD data we have additional saline use entered as 'Hypotension', or there is a log record in the HD data within 30 minutes of a < 90 SBP with a change in bloodflow rate, dialysate flow rate, or ultrafiltration rate (this would include if the HD was stopped).

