The duration of each HD treatment will be adjusted to ensure adequate Kt/V with a reduced flow rate (approximately 4-6 hours at 250 mL/min, 3-4 hours at up to 450 mL/min). During each week determination of HD adequacy will include KtV > 1.2 (calculated from measurements of blood urea) and urea reduction ratio (URR) (weekly URR > 65%).

The most important known potential risk for use of the column is an increased risk of IDH. Risk mitigations may include prophylactic administration of saline, supine positioning/lower limb elevation, avoidance of fasting before HD, avoidance of food intake during HD, use of cooled dialysate, education about the importance of avoiding excessive fluid gain between HD sessions (interdialytic weight gain), and avoiding the use of ultrafiltration rates (UFR) above 13 mL/kg/h. Concomitant medications, especially medications related to or affecting blood pressure (BP), should remain stable while on study and receiving HD with the

The occurrence of IDH events during each week, as outlined in Appendix 17.1: Escalation, De-escalation, and Discontinuation Rules for Treatment with the Column, will be one factor used to determine column size/blood-flow rate escalation/de-escalation as well as discontinuation from the study. There is also a possibility that the blood-flow rate of 450 mL/min cannot be attained due to factors related to the dialysis circuit or other technical issues. If the blood-flow rate of 450 mL/min cannot be attained, it can be adjusted down to enable continued dialysis at a blood-flow rate as high as possible. The reason(s) for the inability to attain a blood-flow rate of 450 mL/min must be documented.

Endpoints:

Primary Endpoints:

- Safety and tolerability of each column size at each blood-flow rate.
 - Evaluation of safety and tolerability will include assessment of the rate and severity of all adverse events (AEs), with analyses of adverse device effects (ADEs), treatment-emergent AEs (TEAEs), number of IDH events, and changes in total and free hemoglobin (Hgb).
 - Tolerability will be assessed by the proportion of subjects who can escalate to and tolerate each column size and blood-flow-rate combination.

Secondary Endpoints

- Weekly Kt/V and URR.
- Total fluid balance for each column-size flow-rate combination.
- Proportion of subjects who are able to achieve the dry weight goal during the allotted HD duration for each column size and flow rate combination.

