4.1 General Considerations

This section presents the statistical approaches that are anticipated for the analysis of the study data. These approaches may at times require modifications due to unanticipated features of the data. Deviations from analyses summarized in this document will be noted in the CSR.

All statistical analyses will be performed using SAS® Version 9.4 or higher, unless otherwise noted.

Data from this feasibility study will be analyzed mostly in a descriptive manner. Limited statistical comparison of outcomes across the various column-size and blood-flow-rate combinations will be performed. Details for any statistical tests are provided in the endpoint analysis sections (4.7, 4.8).

All safety endpoints will be summarized descriptively and tabulated as necessary, unless otherwise stated. Overall baseline and demographic data will be summarized using descriptive statistics.

For analysis of the primary and secondary endpoints, the following will be considered:

- For endpoints that are continuous in nature:
- Number of observations, mean, median, minimum and maximum, and standard deviation (SD) and change from baseline values (or percent change from baseline) will be presented as descriptive summary.
- For endpoints that are categorical in nature:
- Frequency counts and percentages will be presented as descriptive summaries.

Descriptive statistics will be utilized for trial conduct: screen failures, enrollment, withdrawal of consent, and study completion. Primary and secondary endpoints will be assessed at the beginning and end of each week of treatment for a particular column size and blood-flow rate combination. The effect of blood-flow rate will be assessed for a given column size as well as intrasubject and across-subject variability. The sample size was chosen based on clinical consideration of the study designed to test the safety and functionality of the column operated at higher blood-flow rates (up to 450 mL/min).

In general, all summary tables will be supported by a relevant subject data listing. The listings will include all data collected, and will be sorted by subject ID, and actual visit date, as applicable, unless otherwise noted. The listing will also include the column size and blood-flow rate combination as applicable.

Study day 1 is the first day of HD treatment with the day relative to the study day 1.

Statistical Analysis Plan AKST1210-101

Rev. A Page 12 of 28

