Baseline is the first value after the start of HD with the column. For the assessments that do not take place during the treatment weeks (e.g., ECG, physical examination, etc.), the value from Screening will be the baseline. Baseline for lab values will be the last non-missing value prior to the start of HD with the column.

Change from baseline is the post-treatment value minus baseline value.

Subjects who de-escalate (i.e., do not proceed to the next column size and blood-flow rate combination) will only be included in analysis up to the point of de-escalation.

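### SAP 4.1 and 4.9.3 measure change in blood pressure and other vital signs from a value taken after column dialysis has started, and plan no per-subject within-session fall or lowest SBP

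*SAP*

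**What the plan says.** SAP 4.1 gives the default rule: "Baseline is the first value after the start of HD with the column". It makes two exceptions. Assessments not made during the treatment weeks take the screening value, and laboratory values take the last non-missing value before column dialysis starts. SAP 4.7.3 repeats the pre-column rule for total and free hemoglobin.

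SAP 4.9.3 has BP recorded before each session, every 30 minutes during it and at its end. It then plans: "Observed values will be tabulated at baseline, and at each scheduled post-baseline time point". It adds "Change from baseline at each scheduled post-baseline time point will also be summarized" and "Change from baseline in blood pressure will also be presented in figures". The layout comes from SAP 4.9: "Except where indicated, safety parameters will be summarized for the Safety population, by column size and blood-flow rate combination".

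For weight, SAP 4.8.3 uses the session's own starting value: "Change from pre-HD at post-HD per HD session will also be summarized". Low BP is otherwise covered by counts of IDH events per combination (SAP 4.7.2), by a listing in SAP 4.9.3 of repeated SBP below 90 mmHg or action taken, and by the general data listings, of which SAP 4.1 says "The listings will include all data collected".

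**The concern.** The Protocol Summary states: "The most important known potential risk for use of the column is an increased risk of IDH". BP is therefore the vital sign whose reference value matters most. A baseline taken once blood is already passing through the column is not a pre-exposure value. If SBP has dropped by then, the drop is built into the reference and disappears from every reported change. The same rule governs heart rate, respiratory rate and temperature.

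There is also a gap in what is summarised. IDH requires a confirmed SBP below 90 mmHg. A subject who goes from 150 to 95 mmHg for one reading has no IDH event. That fall enters the time-point means and the listings, but no summary shows how far each subject's SBP dropped within a session, or how low it went, by column size and flow rate.

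**Working it through.** **1. The plan's own figure.** SAP 3.3 gives about a 70% chance of at least one IDH event per weekly combination, with 12 subjects and a 10% rate. 1 − 0.9^12 = 1 − 0.282 = 0.718, so it reproduces. At that rate a combination has about a 28% chance of showing no event, so event counts alone carry limited information. The point below does not depend on this figure.

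**2. Which baseline applies to BP.**
- Not made in treatment weeks? No: the schedules in Protocol 15.1 and 15.2 have vital signs at every visit.
- Laboratory value? No.
- The default therefore applies. SAP 3.6 makes Visit 5, Day 1 the first column use, so the baseline is a reading during Visit 5. Read strictly, the run-in readings and the Visit 5 pre-dialysis reading precede baseline and belong neither to baseline nor to the post-baseline time points.

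**3. Effect on the level of change.** Let P be the pre-column value, B = P − d the baseline reading, and Y any later value. The reported change is Y − B = (Y − P) + d. The documents give no BP means or SDs, so d is assumed: 5 to 15 mmHg raises every mean change by 5 to 15 mmHg. For example, with P = 120, B = 110 and Y = 100, the table shows −10 where the change from pre-column is −20.

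**4. What cancels.** In the same subjects:
- Between combinations: (Y2 − B) − (Y1 − B) = Y2 − Y1.
- Within a session from Visit 6 on, if each recording counts as a scheduled time point: (Yt − B) − (Ypre − B) = Yt − Ypre. With Ypre = 120, B = 110 and Yt = 90, the table shows +10 and −20, and the 30 mmHg fall can be recovered.

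**5. Does a same-session reference sharpen the flow-rate contrast?** Assume 12 subjects, t(11) = 2.201, reading SD s = 10 mmHg and between-session SD b. With the study baseline, the SD of the contrast is √(2b² + 2s²). With same-session change it is √(4s²) = 20.0. The 95% half-width is 2.201 × SD / √12.

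| b (mmHg) | SD, study baseline | Half-width, study baseline | Half-width, same-session |
|---|---|---|---|
| 5 | 15.8 | 10.0 | 12.7 |
| 10 | 20.0 | 12.7 | 12.7 |
| 15 | 25.5 | 16.2 | 12.7 |
| 20 | 31.6 | 20.1 | 12.7 |

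Same-session change gains only when b exceeds s, and loses when b is below s.

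**6. What the lowest SBP adds.** Simulation of 400,000 sessions, with 8 readings, SD 10, and 30% of sessions having a 35 mmHg fall at a random start (all assumed):

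| Fall lasts | Largest shift in a time-point mean | Shift in mean lowest SBP |
|---|---|---|
| 1 reading | −1.3 | −6.3 |
| 3 readings | −3.9 | −8.3 |
| To session end | −10.5 | −9.1 |

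Time-point means dilute brief falls that occur at varying times. For sustained falls they do as well or better.

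**7. Biases of the lowest SBP, same assumed SD of 10.** With no true effect, the expected lowest of 6, 8 or 12 readings (3, 4 or 6 hours) is −12.7, −14.2 or −16.3 mmHg. A longer session thus looks 1.6 (4 v 3 hours) to 3.6 mmHg (6 v 3 hours) lower. SAP 3.1 expects about 4–6 hours at 250 mL/min and 3–4 hours at the higher rate. Adding one confirmatory repeat after each reading below 90 lowers the minimum by a further 1.9 to 3.5 mmHg in the cases tried (one reading at a true 85, up to three at a true 80).

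**The case against.** The strongest reply is that little of substance is lost. By step 4 the baseline drops out of every comparison the study is built to make: between column sizes, between flow rates, and between mean BP before and during a session from Visit 6 on. Observed values are tabulated by combination, so the mean paired fall at any time point can be read off for the same subjects. Confirmed SBP below 90 mmHg is counted as a primary analysis, and the low-SBP listing catches saline given for hypotension and flow or ultrafiltration changes near a low reading. The run-in exists to set dialysis duration, not to serve as a BP control. The table shells are separate files not available here, and Protocol 10.4.1 leaves room for further summaries, so a lowest-SBP table may exist.

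Most of this stands. A reader might infer that the baseline rule hides the column's hypotensive effect or biases the flow-rate comparison. The documents do not support that: the shift is common to all combinations, and IDH counts, adverse events and de-escalation reasons do not use this baseline. Nor can one infer that a same-session reference would be more precise; step 5 shows that it may be less so.

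Two things remain. The stated reference for change is a post-exposure value, and unseen shells would not alter that definition. And time-point means give neither the spread of individual falls nor each session's lowest value.

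**Conclusion.** The point holds in limited form and is worth a small correction. As written, the vital-sign baseline falls after exposure has begun, unlike the pre-column baseline the same SAP uses for laboratory values and hemoglobin. The consequence is confined to the level of reported change: if SBP is already down by d at the baseline reading, every mean change is too high by d. The 5 to 15 mmHg range is an assumption, and d could be zero. The missing per-subject fall and lowest SBP matter mainly for brief falls that stay at or above 90 mmHg. This rests on the literal wording of SAP 4.1, on the 30-minute readings counting as scheduled time points, and on the SAP text without its shells. The primary safety analyses stand as planned.

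**What to change.** 1. In SAP 4.1 and 4.9.3, define the baseline for BP and the other vital signs as the last value before the first column session, for example the Visit 5 pre-dialysis reading. This matches the existing laboratory rule and also puts pre-dialysis BP across the weeks on a pre-exposure reference.
2. For intradialytic BP, also summarise change from the same session's pre-dialysis SBP and the lowest scheduled intradialytic SBP. Average each over a subject's sessions and report by column size and flow rate. Show the no-column run-in week alongside, descriptively only.
3. Leave confirmatory repeats out of both measures. Give a first-3-hours version beside the full-session version, because the shorter window removes the reading-count bias but misses late falls.
4. Keep the observed values and the change from the pre-column baseline beside the same-session change, which is the noisier measure if between-session SD is below reading SD.

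The cost is SAP wording, two derived variables and a few more descriptive tables. No new visits or measurements are needed.
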